# 3. STUDY DESIGN

### 3.1. General Description

This study aims to evaluate the efficacy and safety of weekly infusions of efgartigimod IV 10 mg/kg compared to matched-placebo IV in adult participants with post—COVID-19 POTS. This is a randomized, double-blinded, placebo-controlled, parallel-group, phase 2 study. The total study duration is approximately 36 weeks comprising:

- Screening period of approximately 4 weeks
- Treatment period of 24 weeks
- Follow-up period of approximately 8 weeks (56 days ± 3 days) for participants who do not roll over to the open-label extension (OLE) study ARGX-113-2105

42 participants are planned to be randomized to estimate the treatment effect at week 24.

The end of study is defined as the date of the last participant's last visit of treatment period or follow-up period or early discontinuation visit (EDV), as applicable.

#### Treatment and Dosing:

The study population is adult patients with new-onset POTS post—COVID-19. Participant eligibility for trial participation is evaluated based on inclusion/exclusion criteria during screen period. Eligible participants will receive weekly infusions of efgartigimod IV 10 mg/kg or matching placebo in a 2:1 ratio according to randomization. The 10 mg/kg efgartigimod dose is based on body weight, and the maximum total dose per efgartigimod infusion is 1200 mg for participants who weigh ≥120 kg. The dose level will be recalculated if a participant's weight has changed (increased or decreased) by more than 10% from baseline.

Investigational medicinal product (efgartigimod or matching placebo) will be administered during the treatment period in an approximately 1-hour IV infusion once weekly by site staff or a home nurse. IMP administration at home will not commence until after 3 doses have been administered on-site. Any participant who misses a scheduled dose (±2 days) will wait to receive the next scheduled dose.

Document: BIOSdata\argenx\Efgartigimod\HAB40220\Biostatistics\Documentation\SAP

Author: Version Number: 3.0

Version Date: 02 May 2024

Template No.: CS TP BS016 Revision 7 Reference: CS WI BS005

[figure not shown]
Page 16 of 64

The final dose is to be administered at week 23. At week 24, eligible participants may roll over into a single-arm OLE ARGX-113-2105. Participants permanently discontinuing IMP will be ineligible to roll over into the OLE study.

#### Blinding:

This study is double-blinded, and the sponsor/designee, participants, and investigators are blinded to IMP treatment assignment. Investigator can determine whether unblinding of the IMP assignment is necessary in emergencies. The date and reason for the unblinding should be recorded.

### **Table C:** Study Overview

IV=intravenous; OLE=open-label extension

# 3.2. Sample Size

The anticipated width of the 95% CI of the treatment difference on changes from baseline in COMPASS 31 is estimated as follows:

The SD of COMPASS 31 at a single time point in subjects living with POTS is assumed to be approximately with mean score of As the COMPASS 31 scale has favourable test-retest reliability, the Pearson correlation between 2 measurements is assumed to be a minimum of From this, it is estimated that the within-subject SD on COMPASS 31 is approximately from which the SD on the change from baseline is derived to be approximately from the same assuming complete data.

Therefore, the anticipated width (half-width) of the 95% CI is approximately assuming complete data, which could increase to when applying a conservative dropout rate of %. With an anticipated 95% CI half-width COMPASS 31 data from approximately 42 participants will provide sufficient precision to estimate the treatment effect at week 24.

Document: BIOSdata\argenx\Efgartigimod\HAB40220\Biostatistics\Documentation\SAP

Author: Version Number: 3.0

Version Date: 02 May 2024

Template No.: CS\_TP\_BS016 Revision 7 Reference: CS\_WI\_BS005

Page 17 of 64

### 3.3. Schedule of Activities

Schedule of activities can be found in Section 1.3 of the protocol.

### 3.4. Changes to Analysis from Protocol

The protocol mentions mixed model repeated measures as the method of analyzing the Primary endpoints, however the protocol does not mention estimands or Intercurrent events. The SAP considers estimands and intercurrent events. As a result, the main analysis method will be using the mixed model repeated measures and ANCOVA after applying MNAR to missing data from the intercurrent events will be used as supplementary analysis.

The baseline for Questionnaire responses will be the final assessment before the initial administration of IMP up until 3 days post IMP, recorded under baseline visit. The information obtained through this method will be used to inform the development of Phase 3 trials.

### 4. PLANNED ANALYSES

The following analyses will be performed for this study:

- Interim Analysis at the end of treatment phase
- Final Analysis

# 4.1. Data Monitoring Committee

There will be no Data monitoring Committee for this study.

# 4.2.Interim Analysis

One interim analysis will take place for this study once all the participants have either completed the week 12 assessments or discontinued the study prior to week 24. A further interim will be carried out at week 24. Interim analyses identified in this SAP will be performed by IQVIA Biostatistics following authorization of this SAP, database lock and analysis sets. The results of interim analysis week 12 will be based on the unblinded treatment groups by a separate unblinded team who is otherwise not involved within the trial. Section 9.4 of the protocol can be referred to for reference of interim analysis.

Document: BIOSdata\argenx\Efgartigimod\HAB40220\Biostatistics\Documentation\SAP

Author: Version Number: 3.0

Version Date: 02 May 2024

Template No.: CS\_TP\_BS016 Revision 7 Reference: CS\_WI\_BS005

Page 18 of 64

Derivations and definitions for the interim analysis will be based on those required for the final analysis contained in this SAP, unless deviations are stated within the text. The list of outputs provided with the full set of output templates (planned for the final analysis) will highlight which of these outputs will also be provided for the interim analysis.

Access to data will be controlled by access rights to folders where data is stored and manipulated within IQVIA and access to the sFTP used for data transfer.

# 4.3. Final Analysis

All final, planned analyses identified in this SAP will be performed by IQVIA Biostatistics following authorization of this SAP, database lock, analysis sets and unblinding of treatment.

Pharmacokinetic analysis is being performed by the IQVIA Clinical Pharmacology Department in conjunction with BIOS group, PK concentration listings and summary statistics will be described in this SAP. A separate modeling and simulation analysis plan will be prepared to describe planned population PK/PD analysis.

### 5. ANALYSIS SETS

Agreement and authorization of participants included/excluded from each analysis set will be conducted prior to the unblinding of the study.

# 5.1.Enrolled Analysis Set [ENR]

The enrolled analysis set (ENR) will contain all participants who provided informed consent.

# 5.2. Full Analysis Set [FAS]

The full analysis set (FAS) will contain all randomized participants who received at least one dose of IMP and classified as Planned Treatment.

# **5.3.Safety Analysis Set [SAF]**

The safety analysis set (SAF) will contain all randomized participants who received at least one dose of IMP. Data from these participants will be classified according to actual treatment received. The actual treatment arm will be the same as the planned treatment arm unless the participant received IMP other than the planned one

Document: BIOSdata\argenx\Efgartigimod\HAB40220\Biostatistics\Documentation\SAP

Author: Version Number: 3.0

Version Date: 02 May 2024

Template No.: CS\_TP\_BS016 Revision 7 Reference: CS\_WI\_BS005

for the whole study.

### 5.4.PK Analysis Set [PKAS]

The PK analysis set (PKAS) used for the descriptive summaries of efgartigimod serum concentrations will consist of all randomized participants who receive at least one dose of efgartigimod and have at least 1 measured concentration of efgartigimod at a scheduled PK time point after start of dosing without protocol violations or events with potential to affect the PK concentration. Participants in this population will be used for all PK summaries.

When using the FAS, participants will be classified according to their planned treatment arm. For analyses performed on the SAF or PKAS, the actual treatment arm will be considered. The actual treatment arm will be the same as the planned treatment arm unless the participant received IMP other than the planned one for the whole study.

# 6. GENERAL CONSIDERATIONS

# 6.1. Reference Start Date and Study Day

Study Day will be calculated from the reference start date and will be used to show start/stop day of assessments and events. It will appear in every listing where an assessment date or event date appears.

- Reference start date is defined as the day of the first dose of IMP.
- If the date of the event is on or after the reference date, then:
  - $\circ$  Study Day = (date of event reference date) + 1.
- If the date of the event is prior to the reference date, then:
  - o Study Day = (date of event reference date).

In the situation where the event date is partial or missing, the date will appear partial or missing in the listings, and Study Day. Date implies a complete date having day, month and year available. Unless otherwise specified, the *study day* will remain missing when it cannot be calculated due to absence or incompleteness of the concerned and/or reference dates.

Document: BIOSdata\argenx\Efgartigimod\HAB40220\Biostatistics\Documentation\SAP

Author: Version Number: 3.0

Version Date: 02 May 2024

Template No.: CS\_TP\_BS016 Revision 7 Reference: CS\_WI\_BS005

Page 20 of 64

Statistical Analysis Plan

In case the participant never received IMP, the date/time of randomization will be used instead of first IMP administration date/time.

End of study (EOS) is defined as date of participant's last visit. This is date of treatment period completion and/or safety follow-up or early discontinuation visit.

End of treatment (EOT) is defined as date of treatment completion or date of permanent discontinuation of IMP.

### 6.2. Baseline

Unless otherwise specified, baseline is defined as the last available non-missing measurement taken prior to reference start date/time.

Assessments performed on the same day as the first IMP administration but without time information collected or with time information exactly equal to the time of first IMP administration and which are planned predose will be considered as predose.

For parameters related to questionnaires, baseline assessment is the last evaluable assessment before the initial administration of IMP up until within 3 days after IMP, collected gathered during the baseline visit for questionnaires. It includes COMPASS 31, MaPS, PGIC, PGIS, PROMIS (Cognitive Function Short Form 6a, Fatigue Short Form 8a, Global Health Scale score) and EQ-5D-5L.

In case the participant never received IMP, the date/time of randomization will be used instead of first IMP administration date/time.

Adverse Events (AEs) and medications commencing on the reference start date will be considered post-baseline unless otherwise indicated based on available start date/time combination or collected electronic case report form (eCRF) information that identifies the individual event/medication as starting prior to first IMP administration.

# 6.3. Windowing Conventions

All assessments, including unscheduled assessments, will be allocated to analysis visit window. Tables and listings will be based on analysis window defined below. Allocations of assessments will be performed using their relative day.

Document: BIOSdata\argenx\Efgartigimod\HAB40220\Biostatistics\Documentation\SAP

Author: Version Number: 3.0

Version Date: 02 May 2024

Template No.: CS\_TP\_BS016 Revision 7 Reference: CS\_WI\_BS005

Page 21 of 64

Table D: Non-efficacy Analysis Visit Definition

	Target Day	Assigned Study Day (Inclusive)		Week Assigned
		From	To	
Treatment	1	screening	1ª	Baseline
	8	1 b	11	Week 1
	15	12	18	Week 2
	22	19	25	Week 3
	29	26	32	Week 4
	36	33	39	Week 5
	43	40	46	Week 6
	50	47	53	Week 7
	57	54	60	Week 8
	57 + (x*7)	57 + (x*7) - 3	57 + (x*7) + 3	Week 8+x c
Safety	Final dose + 56 days	(Final dose	(Final dose + 56	Week xx+ 56 days
Follow-up		+ 56 days )	days) + 3 days	
		- 3 days		

<sup>a An assessment before the first administration of IMP will be allocated to baseline.

Note: After treatment period ends, safety follow-up will be of approximately 8 weeks (56 days  $\pm$  3 days) for participants who do not roll over to the OLE study ARGX-113-2105.

Some parameters which are not collected at every visits, visit window will be combined (by extending window with previous or subsequent visits).

Document: BIOSdata\argenx\Efgartigimod\HAB40220\Biostatistics\Documentation\SAP

Author: Version Number: 3.0

Version Date: 02 May 2024

Template No.: CS\_TP\_BS016 Revision 7 Reference: CS\_WI\_BS005

<sup>b Post baseline visit Day 1.

c considers value of x, starting from 1 to up until 16 to get visit windows for Week 9 to Week 24.

Page 22 of 64

Table E: Serum Chemistry and hematology, Physical examination, Analysis Visit Definition

	Target Day	Assigned Study Day (Inclusive)		Week Assigned
		From	То	
Treatment	1	Screening	1ª	Baseline
	29	1 b	57	Week 4
	85	58	127	Week 12
	169	128	178	Week 24
Safety	Final dose + 56 days	(Final dose	(Final dose + 56	Week xx+ 56 days
Follow-up		+ 56 days )	days) + 3 days	
		- 3 days		

<sup>a An assessment before the first administration of IMP will be allocated to baseline.

Table F: Immunogenicity, Analysis Visit Definition

	Target Day	Assigned Study Day (Inclusive)		Week Assigned
		From	То	
Treatment	1	screening	1ª	Baseline
	8	1 b	18	Week 1
	29	19	57	Week 4
	85	58	127	Week 12
	169	128	178	Week 24
Safety Follow-up	Final dose + 56 days	(Final dose + 56 days)	(Final dose + 56 days ) + 3 days	Week xx+ 56 days
		- 3 days		

<sup>a An assessment before the first administration of IMP will be allocated to baseline.

Document: BIOSdata\argenx\Efgartigimod\HAB40220\Biostatistics\Documentation\SAP

Author: Version Number: 3.0

Version Date: 02 May 2024

Template No.: CS\_TP\_BS016 Revision 7 Reference: CS\_WI\_BS005

Effective Date: 01Nov2021

Copyright © 2009, 2010, 2012, 2016, 2018, 2019, 2021 IQVIA. All rights reserved. The contents of this document are confidential and proprietary to IQV\$\text{Systemicand} ItsOsidianes.Almouthorized Viscultistibility. All rights reserved. The contents of this document are confidential and proprietary to IQV\$\text{Systemicand} ItsOsidianes.Almouthorized Viscultistibility.

<sup>b Post baseline visit Day 1.

<sup>b Post baseline visit Day 1.

Page 23 of 64

Table G: ECG, Analysis Visit Definition

	Target Day	Assigned Study Day (Inclusive)		Week Assigned
		From	То	
Treatment	1	screening	1ª	Baseline
	8	1 b	46	Week 1
	85	47	127	Week 12
	169	128	178	Week 24
Safety Follow-up	Final dose + 56 days	(Final dose + 56 days ) - 3 days	(Final dose + 56 days ) + 3 days	Week xx+ 56 days

<sup>a An assessment before the first administration of IMP will be allocated to baseline.

Table H: Efficacy Analysis Visit Definition

For MAPS efficacy assessments, the following window will be considered:

Target Day	Assigned Study Day (Inclusive)		Week Assigned
	From	То	
1	screening	3	Baseline
15	4	22	Week 2
29	23	43	Week 4
57	44	71	Week 8
85	72	106	Week 12
127	107	148	Week 18
169	149	178	Week 24

Baseline will be the last assessment before the first administration of IMP (primary consideration) or up to and including 3 days post IMP.

Document: BIOSdata\argenx\Efgartigimod\HAB40220\Biostatistics\Documentation\SAP

Author: Version Number: 3.0

Version Date: 02 May 2024

Template No.: CS\_TP\_BS016 Revision 7 Reference: CS\_WI\_BS005

Effective Date: 01Nov2021

Copyright © 2009, 2010, 2012, 2016, 2018, 2019, 2021 IQVIA. All rights reserved. The contents of this document are confidential and proprietary to IQV**S**ystetingsetro and Its but sidences A pour horized Visculation.

<sup>b Post baseline visit Day 1.

For Modified COMPAS and PROMIS Fatigue efficacy assessments, the following window will be considered:

Target Day	Assigned Study Day (Inclusive)		Week Assigned
	From	То	
1	Screening	3	Baseline
15	4	22	Week 2
29	23	57	Week 4
85	58	127	Week 12
169	128	178	Week 24

Baseline will be the last assessment before the first administration of IMP (primary consideration) or up to and including 3 days post IMP.

Note: Original Compass assessments are not to be included in the baseline calculation..

For PGI-S and PGI-C PROMIS efficacy assessments, the following window will be considered:

Target Day	Assigned Study Day (Inclusive)		Week Assigned
	From	То	
1	screening	3	Baseline
15	4	22	Week 2
29	23	57	Week 4
85	58	106	Week 12
127	107	148	Week 18
169	149	178	Week 24

Baseline will be the last assessment before the first administration of IMP (primary consideration) or up to and including 3 days post IMP.

For PROMIS (Cognition, and efficacy assessments, the following window will be considered:

Target Day	Assigned Study Day (Inclusive)		Week Assigned
	From	To	
1	screening	3	Baseline

Document: BIOSdata\argenx\Efgartigimod\HAB40220\Biostatistics\Documentation\SAP

Author: Version Number: 3.0

Version Date: 02 May 2024

Template No.: CS\_TP\_BS016 Revision 7 Reference: CS\_WI\_BS005

Page 25 of 64

29	4	57	Week 4
85	58	127	Week 12
169	128	178	Week 24

Baseline will be the last assessment before the first administration of IMP (primary consideration) or up to and including 3 days post IMP.

Target Day	Assigned Stu	Assigned Study Day (Inclusive)	
	From	То	
1	screening	1ª	Baseline
85	1 b	127	Week 12
169	128	178	Week 24

<sup>a An assessment before the first administration of IMP will be allocated to baseline.

•	Subject who permanently discontinue the treatment, assessment (COMPASS 31, MaPs, PGI-S and
	PGI-C, PROMIS, Exit Interview,
	will be collected at IMP discontinued visit which will be performed at next
	scheduled visit after discontinuation: EDV visits will be performed within 7 days post final dose for
	those subjects who discontinue study permanently.

Per parameter and analysis window, the non-missing value closest to the target day will be used in the analysis. If more than one non-missing value is located at the same distance from the target day, then the one latest in time will be selected for analysis. The value latest in time will be identified using, in order of preference, the assessment time, the visit label, or group identifier (if applicable). Windowing will be applied to the data prior to any missing data calculations. Questionnaire Total scores and other assessments closest to the target date will be considered for questionnaires.

Document: BIOSdata\argenx\Efgartigimod\HAB40220\Biostatistics\Documentation\SAP

Author: Version Number: 3.0

Version Date: 02 May 2024

Template No.: CS\_TP\_BS016 Revision 7 Reference: CS\_WI\_BS005

<sup>b Post baseline visit Day 1.

Page 26 of 64

### 6.4. Worst-case

A worst-case analysis visit will be created for parameters for which abnormalities and/or toxicity grades (e.g., labs, vital signs, ECGs) are defined to summarize values considered as the worst-case. For abnormalities worst-case is derived per parameter and in case both the lowest and the highest values are considered abnormal, a participant can have two worst-case analysis visits for a same parameter. For toxicity grades the worst-case is the value associated to the highest toxicity grade and is derived per parameter and toxicity direction (hypo / hyper).

All non-missing post-baseline values, including unscheduled assessments will be considered when deriving the worst-case analysis visit.

# 6.5. Treatment-emergent Abnormality/Toxicity

A treatment-emergent abnormality/toxicity (for laboratory assessments, vital signs, or ECGs) is defined as any postbaseline abnormality/toxicity that was not present at baseline (eg, hemoglobin normal at baseline and grade 1 postbaseline; glucose low at baseline and high postbaseline; QTcF [450; 480] ms at baseline and >500 ms postbaseline).

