10.2. Appendix 2: Clinical Laboratory Tests

- The tests listed in Table 2 will be performed as described in the Laboratory Manual.
- Protocol-specific requirements for the inclusion and exclusion of participants are detailed in Section 5.1 and Section 5.2, respectively.
- Additional tests may be performed during the study as determined necessary by the investigator or required by local regulations.
- Investigators must document their review of each laboratory safety report.

Table 2: Protocol-Required Laboratory Tests

Laboratory Test		Paramete	ers
Hematology	RBC count platelet count hemoglobin hematocrit	RBC indices: MCV MCH	WBC count with differential: neutrophils eosinophils lymphocytes basophils monocytes
Serum chemistry	ALT AST albumin ^a BUN	creatinine glucose potassium chloride bicarbonate	sodium total protein ^a calcium bilirubin (total and direct)
Routine urinalysis		blood, ketones, bilirubin, u	urobilinogen, nitrite, leukocyte esterase abnormal)
Pregnancy testing	time points (as needed A high FSH level in t postmenopausal state	d for WOCBP potential, de he postmenopausal range i	onal contraception or hormonal
Specialty laboratory tests	C-reactive protein	ESR	TSH
Other screening tests	10.2.1.3, and Section	CV, HIV (see exclusion or 10.2.1.4, respectively)	riterion 7 and Sections 10.2.1.2,

ALT=alanine aminotransferase; AST=aspartate aminotransferase; BUN=blood urea nitrogen; ESR=erythrocyte sedimentation rate; FSH=follicle-stimulating hormone; hCG=human chorionic gonadotropin; HBV=hepatitis B virus; HCV=hepatitis C virus; MCH=mean corpuscular hemoglobin; MCV=mean corpuscular volume; RBC=red blood cell; TSH=thyroid stimulating hormone; WBC=white blood cell; WOCBP=women of childbearing potential a Results will be blinded.

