# 18.2. Laboratory Evaluations

Results from the central laboratory will be included in the reporting of this study for serum chemistry and hematology, coagulation, urinalysis, serology (eg, viral marker testing), and specialty laboratory parameters. A list of laboratory assessments to be included in the outputs is included in Appendix 2 (Table 2) of the protocol. These are mainly as follows.

**Table K:** Laboratory Assessments

Hematology	RBC count, platelet count, hemoglobin, hematocrit, MCV, MCH, %reticulocytes, WBC count with differential: neutrophils, eosinophils, lymphocytes, basophils, monocytes
Serum chemistry	ALT, AST, albumin, blood urea nitrogen, creatinine, glucose, potassium, chloride bicarbonate, sodium, total protein, calcium, bilirubin (total and direct)
Routine urinalysis	Specific gravity, pH, glucose, protein, blood, ketones, bilirubin, urobilinogen, nitrite, leukocyte esterase, microscopic examination (if blood or protein is abnormal)
Pregnancy testing	Urine test (as needed for WOCBP potential, defined in Section 10.4.1 of the protocol)
Specialty laboratory tests:	CRP, ESR, TSH

Normal ranges are available as provided by the central laboratory and results will be presented in standardized units unless specified otherwise. Clinically significant changes occurring during the study are recorded as an

Document: BIOSdata\argenx\Efgartigimod\HAB40220\Biostatistics\Documentation\SAP

Author: Version Number: 3.0

Version Date: 02 May 2024

Template No.: CS\_TP\_BS016 Revision 7 Reference: CS\_WI\_BS005

Page 54 of 64

AE.

Quantitative laboratory measurements reported as "< X", i.e. BLQ, or "> X", i.e. above the upper limit of quantification (ULQ), will be converted to X for the purpose of descriptive summaries, but will be presented as recorded, i.e. as "< X" or "> X" in the listings. For Toxicity grades the <X and >X will be represented within the scores.

Continuous laboratory parameters will be summarized using descriptive statistics of actual values and changes from baseline at each analysis visit. Categorical parameters will only be listed.

The following summaries will be provided for laboratory data:

Continuous laboratory parameters to be summarized using descriptive statistics of actual values and changes from baseline at each analysis visit for SAF at the IAWK12, IAWK24 and FPA.

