#### 18.2.1. Laboratory Specific Derivations

All datapoints obtained after informed consent up to 60 days after IMP discontinuation or database cutoff will be considered.

The following abnormality categories will be defined:

- Low: value < lower limit of normal range
- Normal: lower limit of normal range  $\leq$  value  $\leq$  upper limit of normal range
- High: value > upper limit of normal range
  - Notes:
  - Classification will be done in standardized units, using non imputed values and limits.
  - For the worst-case analysis visits, as defined in section 6.4, an additional category low + high is defined in case there are both low and high post-baseline values.

Toxicity grades will be computed according to the National Cancer Institute (NCI) common toxicity criteria for

Document: BIOSdata\argenx\Efgartigimod\HAB40220\Biostatistics\Documentation\SAP

Author: Version Number: 3.0

Version Date: 02 May 2024

Template No.: CS\_TP\_BS016 Revision 7 Reference: CS\_WI\_BS005

Effective Date: 01Nov2021

Page 55 of 64

adverse events (CTCAE) toxicity grading list (version 5.0). The implementation of these toxicity grades for analysis is presented in appendix 2. Only the parameters described in appendix 2 will be computed, according to the declared limits for each grade.

Only lab parameters specified within the protocol will be analyzed and, only those both in the protocol and in appendix 2 will be considered for toxicity, all others that are in the protocol and not in appendix 2 but have High/Low/Normal will be presented in the abnormality table.

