# **APPENDIX 2. TOXICITY GRADES**

The table below shows how the CTCAE, v5.0: 27 Nov 2017 will be implemented in the analysis.

Paramater	Unit	Grade 1	Grade 2	Grade 3	Grade 4
Alanine amino transferase		>1-3 *ULN	>3-5 *ULN	>5-20 *ULN	>20 *ULN
Albumin	g/L	<lln-30< td=""><30-20	<20	-	</lln-30<>	<30-20	<20	-
	g/dL	<lln-3< td=""><3-2	<2	-	</lln-3<>	<3-2	<2	-
Alkaline phosphatase		>1.0-2.5 *ULN	>2.5-5.0 *ULN	>5.0-20.0 *ULN	>20.0 *ULN
Aspartate amino transferase		>1-3 *ULN	>3-5 *ULN	>5-20 *ULN	>20 *ULN
Bilirubin (total)		>1.0-1.5 *ULN	>1.5-3.0 *ULN	>3.0-10.0 *ULN	>10.0 *ULN
Calcium (ionized) low	mmol/L	<lln-1.0< td=""><1.0-0.9	<0.9-0.8	<0.8	</lln-1.0<>	<1.0-0.9	<0.9-0.8	<0.8
	mg/dL	<lln-4.0< td=""><4.0-3.6	<3.6-3.2	<3.2	</lln-4.0<>	<4.0-3.6	<3.6-3.2	<3.2
Calcium (ionized) high	mmol/L	>ULN-1.5	>1.5-1.6	>1.6-1.8	>1.8
	mg/dL	>ULN-6.0	>6.0-6.4	>6.4-7.2	>7.2
Calcium (corrected) low	mmol/L	<lln-2.00< td=""><2.00-1.75	<1.75-1.50	<1.50	</lln-2.00<>	<2.00-1.75	<1.75-1.50	<1.50
	mg/dL	<lln-8< td=""><8-7	<7-6	<6	</lln-8<>	<8-7	<7-6	<6
Calcium (corrected)	mmol/L	>ULN-2.9	>2.9-3.1	>3.1-3.4	>3.4
high	mg/dL	>ULN-11.5	>11.5-12.5	>12.5-13.5	>13.5
Creatinine		>1.0-1.5 *ULN	>1.5-3.0 *ULN	>3.0-6.0 *ULN	>6.0 *ULN
Glucose (fasting) low	mmol/L	<lln-3.0< td=""><3.0-2.2	<2.2-1.7	<1.7	</lln-3.0<>	<3.0-2.2	<2.2-1.7	<1.7
Potassium low	mmol/L	-	<lln-3.0< td=""><3.0-2.5	<2.5	</lln-3.0<>	<3.0-2.5	<2.5
	mEq/L	-	<lln-3.0< td=""><3.0-2.5	<2.5	</lln-3.0<>	<3.0-2.5	<2.5
Potassium high	mmol/L	>ULN-5.5	>5.5-6.0	>6.0-7.0	>7.0
	mEq/L	>ULN-5.5	>5.5-6.0	>6.0-7.0	>7.0
Sodium low	mmol/L	<lln-130< td="">-	<130-120	<120	</lln-130<>	-	<130-120	<120
	mEq/L	<lln-130< td="">-	<130-120	<120	</lln-130<>	-	<130-120	<120

Document: BIOSdata\argenx\Efgartigimod\HAB40220\Biostatistics\Documentation\SAP

Author: Version Number: 3.0

Version Date: 02 May 2024

Template No.: CS\_TP\_BS016 Revision 7 Reference: CS\_WI\_BS005

Page 62 of 64

Paramater	Unit	Grade 1	Grade 2	Grade 3	Grade 4
Sodium high	mmol/L	>ULN-150	>150-155	>155-160	>160
	mEq/L	>ULN-150	>150-155	>155-160	>160

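### SAP Section 6.5 uses a hemoglobin grade as its example of treatment-emergent toxicity, but Appendix 2, the only list from which laboratory grades are computed, has no hemoglobin row

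*SAP*

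**What the plan says.** Laboratory changes belong to the primary safety endpoint (SAP Table A and Section 18). Four places govern how hemoglobin is handled.

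- **SAP Section 6.5** defines a treatment-emergent toxicity as one seen after baseline but absent at baseline. Its first example is "hemoglobin normal at baseline and grade 1 postbaseline".
- **Protocol Section 10.2, Table 2** requires the test; the hematology entry reads "RBC count platelet count hemoglobin hematocrit". **SAP Table K** repeats it: "RBC count, platelet count, hemoglobin, hematocrit, MCV, MCH".
- **SAP Section 18.2.1** restricts grading: "Only the parameters described in appendix 2 will be computed", and "only those both in the protocol and in appendix 2 will be considered for toxicity". Protocol parameters outside the appendix that "but have High/Low/Normal will be presented in the abnormality table" form the remaining group.
- **SAP Appendix 2** sets out how CTCAE version 5.0 is implemented. Its hematology rows are lymphocytes (low and high), neutrophils (low), platelets and white blood cells.

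SAP Section 18.2 plans cross-tabulations of toxicity grade against baseline grade, at each post-baseline analysis visit and at the worst case, in the safety analysis set at IAWK12, IAWK24 and the final planned analysis.

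**The concern.** Section 6.5 and Section 18.2.1 with Appendix 2 cannot both be followed. A programmer who obeys Section 18.2.1 cannot produce the very case that Section 6.5 uses to explain the concept, because no hemoglobin grade would exist at any visit.

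What is at stake is how severity is displayed. Without a grade, hemoglobin is categorized only as Low, Normal or High. In the categorical shift and worst-case tables, a value just under the lower limit of normal and one far below it fall in the same cell. Platelets, neutrophils, lymphocytes and white blood cells, from the same blood count, are graded.

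**Working it through.** The plan states no figure to reproduce. The check compares Appendix 2 with the list of collected analytes and then applies the Section 18.2.1 rule.

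**Inputs**

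- Collected analytes, from protocol Table 2 and SAP Table K: 12 hematology (RBC, platelets, hemoglobin, hematocrit, MCV, MCH, WBC and five differential counts) and 14 serum chemistry (ALT, AST, albumin, BUN, creatinine, glucose, potassium, chloride, bicarbonate, sodium, total protein, calcium, total bilirubin, direct bilirubin). 12 + 14 = 26. Percent reticulocytes, seen only in Table K, is left out of the count.
- Appendix 2 rows, counted as parameter by direction: 15 chemistry and 5 hematology. 15 + 5 = 20.

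**Step 1: match the rows to what is collected.** Of the 20 rows, 14 correspond to an analyte in the form listed. The other 20 − 14 = 6 do not:

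- "Alkaline phosphatase" (1 row) is in neither Table 2 nor Table K.
- Ionized calcium (2 rows, the first being "Calcium (ionized) low") and corrected calcium (2 rows): the lists name only calcium, and the SAP gives no correction formula.
- Fasting glucose, low (1 row): the lists name only glucose.

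**Step 2: apply the rule that a parameter must be in both the protocol and Appendix 2.**

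- Strict reading, exact form required: ALT, AST, albumin, total bilirubin, creatinine, potassium, sodium, lymphocytes, neutrophils, platelets and WBC are graded, so 11 of 26.
- Lenient reading, accepting collected calcium and glucose for the corrected and fasting rows: 11 + 2 = 13 of 26.
- The remaining 26 − 13 = 13 analytes have no row on either reading. Hemoglobin is one of them.

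**Step 3: trace hemoglobin through the planned outputs.**

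- Toxicity shift and worst-case tables (SAP 18.2): absent.
- Treatment-emergent toxicity (SAP 6.5): cannot be derived. Treatment-emergent abnormality, such as Normal to Low, can.
- Actual values and changes from baseline by visit (SAP 18.2), with minimum and quartiles (SAP 7.2): present.
- Low/Normal/High shift tables, including worst case (SAP 18.2 and 18.2.1): present.
- Listing of participants with any post-baseline abnormality (SAP 18.2): present.
- Adverse events: present where the investigator judges the change clinically significant (protocol 8.3.4), graded by CTCAE version 5.0 (protocol 10.3.3, SAP 18.1).

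**Step 4: effect of adding the row.** Gradable analytes rise from 11 to 12 of 26 on the strict reading, or from 13 to 14 on the lenient one. No design or efficacy figure changes.

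**The case against.** The strongest reply is that Section 6.5 offers only an illustration of a generic definition that also covers vital signs and ECGs. It does not list which analytes are graded. Section 18.2.1 gives an explicit route for parameters outside Appendix 2, half of the 26 analytes take it, and the choice of analytes to grade in a phase 2 trial is partly preference. Changing the example would also remove the conflict. This stands in part: it makes the matter small. It does not remove it, because hemoglobin is the one analyte that the SAP itself describes as graded, and nothing says that it was left out on purpose.

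A reader might infer that anemia is missing from the safety reporting. The documents do not support that. Step 3 shows hemoglobin in four other kinds of output, and the minimum in the descriptive tables would reveal a severe fall. Those outputs do not, however, count participants by laboratory grade, and the adverse event route depends on the investigator's judgment.

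A reader might also infer that the plan will grade analytes that are not collected. It will not: the two-part rule in Section 18.2.1 makes the alkaline phosphatase row inert, and the ionized calcium rows too if ionized calcium is not measured. Nor do these rows cause the hemoglobin gap; they are a separate matter. A claim that fasting glucose is unavailable is likewise unproven. Protocol Section 5.3.1 sets no meal restriction, but the laboratory manual, which might specify fasting, is not among the documents.

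Finally, Appendix 2 crosses a page and its cells are damaged in extraction. A hemoglobin row would fall alphabetically just before lymphocytes, near a break in the extracted text. Nothing there marks a lost row, but the point should be confirmed in the original PDF.

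**Conclusion.** The inconsistency holds on the text. As written, hemoglobin falls are not severity-graded in the laboratory toxicity shift and worst-case tables at IAWK12, IAWK24 and the final analysis. The gap is one analyte in one family of tables within the primary safety endpoint. It does not touch efficacy, sample size or design, and hemoglobin remains visible elsewhere in the safety output. It is worth correcting because it changes a planned output at almost no cost, but it is a minor point.

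The conclusion assumes that the extracted Appendix 2 is complete and that Section 18.2.1 is applied literally. The mismatched calcium and glucose rows leave their handling to the programmer, which is secondary. The inert rows affect no result.

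**What to change.** After checking the original PDF, add a hemoglobin (low) row to SAP Appendix 2, with limits taken directly from the CTCAE version 5.0 that the appendix already cites, and include hemoglobin in the toxicity tables. The limits are not in the documents reviewed, so none are given here. Changing the Section 6.5 example and stating that hemoglobin is not graded would restore consistency, but would leave the severity of falls undisplayed.

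As secondary tidying:

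- State how collected calcium maps to the corrected rows, with the formula. Albumin is also collected, so an albumin-based correction could be derived.
- State how collected glucose maps to the fasting row, including what is done when fasting status is unknown.
- Remove the alkaline phosphatase row and, if ionized calcium is not measured, those rows as well. This has no effect on results.

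The cost is one table row, a few sentences and a small program change. No new data are needed: the protocol's schedule of activities already has hematology at screening, baseline and weeks 4, 12 and 24. If the change is made after unblinding, label it post hoc.
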